6.2 Rationale for Choice of Hypothesis

As the OPC presented in Table 1, Valve Thrombosis, Major Hemorrhage and Major PVL rate are all less than 1.2% per patient-year, and to achieve the 80% power for these tests, a much larger sample size is required to evaluate these rare events. For example, to detect a Major Paravalvular Leak rate of 0.6% per patient-year, more than 1800 patient-years of data are required; and to detect a Valve Thrombosis rate of 0.2% per patient-year, more than 5000 patient-years of data are required. Such a large sample size requirement may leave the trial un-executable. Thus, the smallest acceptable adverse event rate of 1.2% per patient-year (excluding Valve Thrombosis, Major Hemorrhage and Major PVL) is chosen for the sample size assumption.

7. Statistical Methods

7.1 Study Subjects

7.1.1 Disposition of Subjects

Subjects disposition will be summarized, including the number of subjects enrolled/implanted, died, explanted, withdrawn, lost-to follow up, and completed each visit during the study.

7.1.2 Clinical Investigation Plan (CIP) Deviations

A protocol deviation is defined as an event within a study that did not occur according to the CIP or Clinical Trial Agreement. Protocol deviations will be reported regardless of whether they are preapproved by Medtronic. Deviations will be summarized by type for each interval. The percent of subjects with the deviations will be calculated based on the number of subjects eligible for the specified visit.

7.1.3 Analysis Sets

The primary analysis will be performed on the implanted population (as treated population). The implanted population consists of all enrolled subjects who are actually implanted with the Model 400 valve. To be considered implanted, the subject's device disposition form must show at least one device with a final disposition of "Implanted." Time zero begins at the date of the procedure.

The data from the subjects with attempted procedures, but who were not implanted with the Model 400 valve will be summarized separately and reported as descriptive statistics. The subjects with attempted procedures will not be counted towards the total number of implants.

The subjects with TAV in SAV procedures are identified as TAV-in-SAV population. The TAV in SAV population includes all patients who had Implantation of transcatheter valve within Model 400 Valve (valve in valve) from valve reintervention eCRF. The hemodynamic results after explant or TAV-in-SAV procedures won't be included in the hemodynamic tables for the main cohort. A separate analysis for TAV-in-SAV cohort will be created on an ad-hoc basis.

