4.4.3 Attempted Procedure

An attempted procedure is one where the trial subject has entered the Operating Room/Theater and the Investigator intends to implant the Model 400 valve, but the trial subject does not receive the Model 400 valve. The procedure could be aborted either before or during the attempted valve implant, or due to additional subject anatomic/medical considerations which would preclude the use of the Model 400 valve, or the Investigators' decision to use a product other than the Model 400 valve.

If the Model 400 valve (or accessories) passes the plane of the body, but the Model 400 valve is not implanted, the subject will be followed for safety reporting only for 30 days post-attempted implant, and then exited from the trial. AE data should be collected on the AE eCRF, and trial exit data on the Trial Exit eCRF.

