4.4.4 Valve Reintervention

Any intervention post-index procedure, which is required to repair, remove, alter, or replace a previously implanted Model 400 valve is considered a valve reintervention. All Model 400 valve reinterventions are considered prosthesis-related. The details of a reintervention should be collected on a Reintervention eCRF and the reason for the reintervention should be collected on an AE eCRF.

If a subject's study valve is explanted, the subject will be followed for safety reporting only for 30 days post-explant. AE data should be collected on the AE eCRF, and trial exit data on the Trial Exit eCRF.

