6.4 Echocardiography

Transthoracic echocardiography (TTE) is required at baseline, discharge (up to 30 days), and all in-office scheduled follow up visits. The site will record echocardiography data on the Site Echo eCRF.

A peri-procedural Transesophageal Echocardiogram (TEE) is required before the subject leaves the operating room/theater to assess the valve implant and evaluate/characterize any paravalvular leak and peak /mean gradient. The site will record the TEE data on the Implant eCRF.

All TTE exams will be sent to the Echo Core Lab for central assessment; the Echo Core Lab will record the central assessment on the Echo Core Lab Assessment eCRF.

Details of the Echocardiography methods are provided in Appendix G: Echocardiographic Procedures. Additional information regarding the Echo Core Lab can be found in Section 16.1.

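### Defining the implanted set by final device disposition drops a subject whose only Model 400 is seated and removed in the same operation from the early event rates and Kaplan-Meier summaries

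*SAP*

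**What the plan says.** **Who is analysed.** SAP 7.1.3 makes the implanted (as-treated) population primary and sets a subject-level test: "the subject's device disposition form must show at least one device with a final disposition of" Implanted. Time zero is the procedure date. For everyone else who reached the operating room, "The subjects with attempted procedures will not be counted towards the total number of implants"; SAP 7.1.3 and 7.9.1.3.2 give them a separate descriptive summary.

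**What an attempted procedure is.** Under Protocol 4.4.3, "the Investigator intends to implant the Model 400 valve, but the trial subject does not receive the Model 400 valve". The same section adds: "The procedure could be aborted either before or during the attempted valve implant". If the valve or an accessory entered the body "but the Model 400 valve is not implanted, the subject will be followed for safety reporting only for 30 days post-attempted implant".

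**When a problem may be found.** Protocol 6.4 says a transesophageal echo (TEE) "is required before the subject leaves the operating room/theater to assess the valve implant and evaluate/characterize any paravalvular leak".

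**What counts as a reintervention.** Protocol 4.4.4: "Any intervention post-index procedure, which is required to repair, remove, alter, or replace a previously implanted Model 400 valve is considered a valve reintervention". Protocol 4.4.2 defines the index procedure as the one in which the Model 400 is implanted.

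**How early results are formed.** SAP 7.9.1.3.1 divides events up to and including day 30 by the total number of subjects. Kaplan-Meier estimates start at time zero, with 30 days as the first reported point (SAP 7.2.2.4).

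**The concern.** The TEE takes place before the subject is classified. If it shows a leak or poor function and the surgeon takes the Model 400 out and places another manufacturer's valve, that finding moves the subject out of the primary set. Membership then depends on an outcome of the operation, and the subjects removed are those with the earliest device failures.

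PVL, explant and reintervention are named safety endpoints. Their early rates and Kaplan-Meier curves go into the PMA report, the CE mark report and the main manuscript, all of which this SAP governs (7.2.1). A reader of those tables would take them to describe what happens when a surgeon sets out to implant this valve and seats it. They would in fact describe what happens once a Model 400 has stayed in place to the end of the operation.

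**Working it through.** The plan states no figure for this point. The check traces the definitions through three cases and then sizes the effect on assumed counts.

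**Case 1: the only Model 400 is seated, removed in the same operation, and a non-study valve is placed.** On the natural reading no device ends as Implanted, so SAP 7.1.3 excludes the subject and Protocol 4.4.3 makes the case an attempted procedure. The removal and its cause are outside the early rates and Kaplan-Meier summaries. The explant exit row of Protocol Table 2 names a Valve Reintervention form; the row for device contact without implant does not.

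**Case 2: the first Model 400 is removed and a second is left in.** One device ends as Implanted, so the subject stays in. The first removal happens within the index procedure, not after it, so Protocol 4.4.4 bars it from being a reintervention. Whether it is an explant, or its leak an early PVL event, turns on Appendix E, which is not in the available text.

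**Case 3: PVL is seen and the valve stays in.** The subject is in the set, and nothing in SAP 7.9.1.3.1 excludes an event on day 0. It can count.

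**Size for case 1.** Inputs:
- N = 1300, the maximum number of implants (SAP 5). Attempted subjects do not count towards it, so removals add to the denominator. N = 650 is the earlier target in SAP 6.1.
- x = same-operation removals with no second Model 400: assumed, because the documents give none.
- y = early explants already counted: assumed 0 or 5.

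The rate as written is y/N. The rate with removals counted is (y + x)/(N + x).

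| N | y | As written | x = 1 | x = 3 | x = 6 | x = 13 |
|---|---|---|---|---|---|---|
| 1300 | 0 | 0.00% | 0.08% | 0.23% | 0.46% | 0.99% |
| 1300 | 5 | 0.38% | 0.46% | 0.61% | 0.84% | 1.37% |
| 650 | 0 | 0.00% | 0.15% | 0.46% | 0.91% | 1.96% |

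For example, 13/(1300 + 13) = 0.99% and (5 + 13)/(1300 + 13) = 1.37%.

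**Size for case 2.** The subject is already in N, so an uncounted removal shifts the rate by x/N: 1/1300 = 0.08% up to 13/1300 = 1.00%.

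**Direction.** For explant, (y + x)/(N + x) exceeds y/N whenever y < N, so exclusion can only lower the reported rate. For early PVL, exclusion lowers the rate if the share of removals due to leak exceeds the early PVL rate among those implanted, which is plausible when TEE looks for leak.

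**Late tests.** The OPC comparison uses late events over late patient-years. Case 1 subjects add neither, so it does not move.

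**The case against.** The as-treated set is an explicit choice in the protocol (Section 7), and these subjects are not hidden. Those with device contact have 30 days of safety follow-up, an Implant form, a discharge or 30-day form with labs and echo, and adverse event forms (Protocol 4.4.3, Table 2). They get a separate summary, and SAP 7.10 lists all adverse events, device deficiencies, reinterventions, explants and deaths. Protocol Section 7 also brings their operative mortality into the overall safety analysis. No hypothesis test is affected, and explant and reintervention have no OPC. Pooling subjects who leave with another manufacturer's valve could charge that valve's events to the Model 400. All of this stands. It is why the remedy should be supplementary and should stop attributing valve-related events once the valve is out.

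Three stronger readings are tempting, and the documents do not support them:
- *That failures seen on the TEE never count.* PVL in a valve left in place can be an early event, and a subject given a second Model 400 remains in the set.
- *That a same-operation removal is never an explant.* The reintervention wording excludes it from that endpoint only. Explant and PVL are defined in Appendix E, and the codes on the disposition form are not shown. Protocol 11.5.1 lists implanted, disposed of and returned, but for site device records, which are not shown to be the form the SAP names.
- *That explants are understated by some given fraction.* That needs both a removal rate and a later explant rate, and the documents give neither.

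The objection does not answer the main point. A separate summary and listings do not put these removals into the early rates, and the SAP has no rule for a valve seated and then removed in one operation.

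**Conclusion.** The point holds in a limited form. The rule in SAP 7.1.3 selects on the outcome of the operation: case 1 subjects leave the early rates and Kaplan-Meier summaries, and case 2 removals have no defined place among the endpoints. The resulting bias in the descriptive early explant rate, and probably in early PVL, favours the device. If 1 to 13 removals are assumed alongside 1300 implants, an early explant rate of 0% would become about 0.1% to 1.0%; if there are no such removals, nothing changes. The conclusion rests on the natural reading of final disposition and, for case 2, is subject to Appendix E.

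A related gap needs no assumption. The SAP's sections on attempted subjects (7.1.3 and 7.9.1.3.2) omit the operative-mortality sub-analysis that Protocol Section 7 requires, although SAP 7.11 declares the plan consistent with the protocol.

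**What to change.** Keep the implanted set as primary, and unchanged for the late OPC tests and hemodynamics. In SAP 7.1.3 and 7.9.1.3.1:

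1. State how a Model 400 that is seated and then removed in the same operation is dispositioned, with or without a second Model 400.
2. Add supplementary early rates (up to day 30), with matching Kaplan-Meier estimates, over all subjects in whom a Model 400 was seated. Count a same-operation removal as an early explant and its adjudicated cause, such as PVL, as an early event.
3. For subjects left with a non-study valve, censor at removal for later valve-related events.
4. Add the protocol's operative-mortality sub-analysis of attempted subjects, so that deaths in this group are still reported.

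The cost is SAP wording and a little more analysis. The Implant, adverse event and 30-day forms already cover subjects with device contact; the sponsor should confirm that they separate a valve that was seated from one that only entered the field. The downside is that early rates may look slightly less favourable.

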7.2.2.4 Kaplan-Meier Analyses

Kaplan-Meier analysis of event-free rates (or event rates) will be performed at 30 days, 6 months, 12 months and annually through five years. These times correspond to 30 days, 180 days, 365 days, 730 days, 1095 days, 1460 days, and 1825 days, respectively. At each time point with data, the product-limit estimate of the event-free rate (or event rate), the number of subjects at risk, the number of

Revision 7.0

Page 11 of 22

subjects with events, the number of subjects censored, and the loglog transformed 95% confidence interval using the Greenwood standard error will be presented.

For subjects without an event, the date of censoring will be the latest date of all follow-up visits, assessments, and events (including death).

7.2.2.5 17 mm and 29 mm Valves

If at the time of PMA and CE mark submissions, PERIGON Pivotal trial does not have fifteen 17mm subjects successfully implanted with Model 400 valve and followed for at least one year, 17mm study data from PERIGON Japan Trial will be utilized to support 17mm market approval in United States and other global geographies.

The PERIGON Japan Trial with 17mm valve is a prospective, interventional, non- randomized, multisite trial to evaluate the safety and effectiveness of the 17mm aortic bioprosthesis in a patient population undergoing surgical aortic valve replacement with the similar inclusion and exclusion criteria as the PERIGON Pivotal trial.

Similarly for 29 mm valve, if at the time of PMA and CE mark submission, PERIGON Pivotal trial does not have fifteen 29 mm subjects successfully implanted with Model 400 valve and followed for at least one year, the enrollment may continue for 29 mm subjects until the regulatory requirement is met.

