7.4 Handling of Missing, Unused, and Spurious Data and Dropouts

Every effort will be undertaken to minimize missing data. In time-to-event outcomes, dropouts will be censored at the time of discontinuation, consistent with the Kaplan-Meier approach. Unless specified otherwise in each objective, no statistical techniques will be used to impute missing data. If a subject's data are missing for any reason, that subject will not be included in that portion of the analysis. The number of subjects included in each analysis will be reported so that the potential impact of missing data can be assessed.

In the case of partial dates, the general rule is as follows:

- If only the month and year are known, the event or assessment will be analyzed as if it occurred on the 15th of that month.
- If only the year is known, the event or assessment will be analyzed as if it occurred on June 30th of that year.

These resolutions of partial dates are subject to the restrictions that pre-procedure events and assessments must occur between the enrollment date and the procedure date, and post-procedure events and assessments must occur no earlier than the procedure date. If additional information about the partial dates might be known, for example, the event occurs after 15th of the month, then data may be analyzed as if it occurred on the 16th of the month.

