7.9.1.3.2 Determination of Data for Analysis

All subjects who are enrolled in the trial and have a trial valve implanted will be included for analysis.

For subjects who are attempted but not implanted, their data will be summarized separately.

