7.9.2.3 Data Collection and Analysis Methods

NYHA functional classification and hemodynamic data will be summarized using descriptive statistics for continuous variables and frequency tables for discrete variables.

NYHA functional class will be evaluated based on the percentage of subjects in each specific NYHA class at each postoperative time-point and the percentage of subjects at each postoperative time-point who have improved, worsened, or not changed in NYHA class compared to preoperative baseline.

Medtronic PERIGON Pivotal Trial Statistical Analysis Form Plan Revision 7.0 Page 20 of 22 Medtronic

All echocardiograms will be analyzed by an echo core lab which will determine the values for the Hemodynamic Performance endpoints. Valvular regurgitation will be summarized with a frequency table for each visit interval and the other Hemodynamic Performance endpoints will be summarized as with continuous data. For each subject with paired data, the change from baseline may also be calculated at discharge (or 30 days), 3-6 months, 1 year and annually thereafter through 5 years. These data will be summarized by valve size.

Control articles based on current literature of previously approved heart valves will be selected. Effectiveness data from the control articles will be provided so as to inform the reader of the current state of heart valve technology, as expressed by articles in quality peer-reviewed journals, to allow for evaluation of the Model 400 valve effectiveness data.

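### After TAV-in-SAV the SAP drops the hemodynamic results but keeps NYHA class from the same visits, so symptom relief from a second valve can count as Model 400 improvement

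*SAP*

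**What the plan says.** SAP 7.1.3 takes all implanted subjects as the analysis set: "The primary analysis will be performed on the implanted population (as treated population". It then defines a TAV-in-SAV population from the valve reintervention eCRF and gives one rule for what follows the procedure: "The hemodynamic results after explant or TAV-in-SAV procedures won't be included in the hemodynamic tables for the main cohort". For the subjects concerned it adds only: "A separate analysis for TAV-in-SAV cohort will be created on an ad-hoc basis".

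The other places that bear on data after the procedure are these.

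- **NYHA (SAP 7.9.2.3).** The table gives the percentage in each class and "the percentage of subjects at each postoperative time-point who have improved, worsened, or not changed in NYHA class", compared with the preoperative baseline. Nothing stops it at TAV-in-SAV. SAP 4.2.1 and 7.9.2.1 list NYHA and hemodynamic performance as separate endpoints, so a rule about hemodynamic tables does not reach NYHA.
- **Kaplan-Meier (SAP 7.2.2.4).** "For subjects without an event, the date of censoring will be the latest date of all follow-up visits, assessments, and events (including death".
- **Linearized rates (SAP 7.9.1.3.1 and 7.9.1.3.2).** Late events are divided by late post-operative patient-years, and "All subjects who are enrolled in the trial and have a trial valve implanted will be included for analysis".
- **Missing data (SAP 7.4).** "If a subject's data are missing for any reason, that subject will not be included in that portion of the analysis". The number in each analysis is to be reported.
- **Follow-up (Protocol 4.4.4 and Table 2).** Explanted subjects have 30 days of safety-only follow-up and then exit. A valve-in-valve procedure is not among the exit scenarios.
- **Disposition (SAP 7.1.1).** Deaths, explants, withdrawals and losses are counted. TAV-in-SAV is not named.

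**The concern.** Once a transcatheter valve sits inside the Model 400, the working leaflets belong to another device. The SAP accepts this for echo data, which it no longer treats as Model 400 performance. It does not accept it for the NYHA class recorded at the same visit, which stays in the main table as Model 400 effectiveness. No reason is given for treating the two halves of one objective differently.

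The inconsistency has a direction. From the procedure onward a failed valve leaves the hemodynamic tables, while any relief brought by the second valve can enter the NYHA table as improvement over the preoperative state. This matters most for the late visits in the final report and the main manuscript, both of which SAP 7.2.1 covers, because that is where such procedures accumulate. The same silence leaves time on the second valve inside the risk time for valve-related events.

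**Working it through.** **1. Which data survive the procedure under the plan as written**

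| Output | Rule after TAV-in-SAV | Basis |
|---|---|---|
| Hemodynamic tables | Removed | Stated, SAP 7.1.3 |
| NYHA table | Kept | No rule, SAP 7.9.2.3 |
| Kaplan-Meier time, subject without that event | Continues to last contact | Stated, SAP 7.2.2.4 |
| Late patient-years | Continue | No rule, SAP 7.9.1.3.1 |

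That these subjects remain on the visit schedule is inferred from Protocol 4.4.4 and Table 2, which shorten follow-up for explant only.

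**2. The plan's own sample size figure**

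Inputs (Protocol 7.1.1.3, SAP 6.1): one-sided alpha 0.05, power 80%, true rate 1.2% and null rate 2.4% per patient-year, 5% annual attrition.

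- The smallest T with P(E ≤ n | 0.024T) ≤ 0.05 and P(E ≤ n | 0.012T) ≥ 0.80 is T = 811 with n = 12 (power 0.816). This is close to the stated 800.
- Uniform accrual over one year, 1 to 2 years of follow-up and 5% attrition give 1.442 patient-years per implant, so 556 implants give 801.6 patient-years.

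Both figures reproduce, and this point does not dispute them.

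**3. NYHA**

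Assumptions, because the documents give no TAV-in-SAV rate: 1-4% of 1300 implanted, all assessed at 5 years and all improved; 70% improved overall; a table of 1000 subjects. The last is in line with 5% annual attrition: 1300 × 0.95^5 = 1006.

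- Number of subjects k = 1300 × 0.01 to 1300 × 0.04 = 13 to 52.
- Percent improved after excluding them = (700 − k)/(1000 − k).
- k = 13: 687/987 = 69.6%, a fall of 0.4 points.
- k = 52: 648/948 = 68.4%, a fall of 1.6 points.

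For this range of k these are upper limits. If the TAV-in-SAV subjects had improved at the same 70% as the rest, the exclusion would change nothing.

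**4. Patient-years**

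Five-year total for 1300 subjects: 1300 × (1 − 0.95^5)/(−ln 0.95) = 5733. The numbers of subjects and years below are assumptions.

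- 0.5% of 1300 with 1 year each: 6.5 patient-years, or 0.1%.
- 3% of 1300 with 3 years each: 117 patient-years, or 2.0%.
- 1-4% of 1300 with 1.5 years each: 19.5 to 78 patient-years, or 0.3-1.4%, which lies inside that range.

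**5. Effect on an OPC test**

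The Cox upper bound in SAP 7.9.1.3.1 is taken as χ²(0.95, 2n+1)/(2Y). With n = 12 events and Y = 800 it is 2.353%, below the limit of 2.4%. Suppose all 12 events precede the procedure and a share s of patient-years is removed.

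| s | Upper bound |
|---|---|
| 0.5% | 2.365% |
| 1% | 2.377% |
| 2% | 2.401% |

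The result at 12 events flips only when s exceeds 1.95%, which is the extreme end of the assumed five-year range. The PMA data are cut at the first date with 800 patient-years (SAP 7.2.2.1), when follow-up is shorter.

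The opposite case is as easy to build. With 13 events in 800 patient-years the bound is 2.507%, which fails. If one of the 13 occurred after TAV-in-SAV, ending time at the procedure and losing 1% of patient-years leaves 12 events and a bound of 2.377%, which passes.

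**The case against.** The hemodynamic rule is itself sensible: echoes taken through a second valve do not describe the Model 400, and those recorded before the procedure stay in the tables. A reader might infer that failed valves disappear from the report. They do not. The TAV-in-SAV is a valve reintervention under Protocol 4.4.4. Reintervention, structural deterioration and non-structural dysfunction are safety endpoints, and SAP 7.10 lists every reintervention, explant and death. A subject whose failure was recorded as, say, structural deterioration has already had the event in that curve.

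A reader might also infer that every gap favours the valve. For event rates this is not established. Time on the second valve adds to the denominator, but a leak or thrombosis after the procedure can add to the numerator. The Model 400 also stays in the body, so later endocarditis or thromboembolism may still belong to it. Outright censoring could remove such events and would be informative. Keeping events after reintervention is a defensible main analysis.

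A third inference is that the paired comparison hides deterioration because it refers to the preoperative valve: "For each subject with paired data, the change from baseline may also be calculated at discharge (or 30 days), 3-6 months, 1 year". That comparison is optional, and hemodynamics are summarized by valve size and visit (Protocol 7.1.2.2), so a rise in gradient between early and late visits would show.

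Finally, effectiveness carries no hypothesis, so no test depends on the NYHA table. All of this stands and limits the point. None of it explains why the echo from a visit is removed while the NYHA class from that visit is kept.

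**Conclusion.** The inconsistency is real and follows from the text. For Kaplan-Meier time it rests on a written censoring rule. For NYHA and patient-years it rests on the absence of one. It concerns TAV-in-SAV. Explant is largely moot because those subjects leave the trial after 30 days.

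Its size is modest. Under the assumptions in the working, the late percent improved in NYHA is overstated by at most about 0.4-1.6 points. The effect on the OPC tests is about 0.1-2.0% of patient-years and has no fixed sign. Every one of these figures depends on assumed TAV-in-SAV frequencies.

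A reader could reach 1.3-5.2 points by dividing 13 to 52 subjects by 1000, but that scores each of them as a failure and not as excluded, which is a different estimand. Rescaling the NYHA percentage to all implanted subjects answers a question about death and explant, not about TAV-in-SAV. The documents support neither as the size of this problem. The point is worth correcting for the five-year effectiveness tables and does not threaten the safety conclusions.

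**What to change.** 1. In SAP 7.1.3 and 7.9.2.3, apply the existing hemodynamic cut to NYHA from the date of TAV-in-SAV or explant. Beside the NYHA and hemodynamic tables, show at each visit the numbers dead, explanted, with TAV-in-SAV and not assessed.
2. Keep the planned linearized rates and Kaplan-Meier analyses for valve-related events. Add a sensitivity analysis that ends late patient-years and Kaplan-Meier time at TAV-in-SAV, after counting the event that led to it.
3. List the last echo values before explant or TAV-in-SAV. Paired change from the first post-operative echo would be a useful optional addition.

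The data are already collected on the reintervention eCRF and at scheduled visits. The cost is SAP wording, a few table rows and possibly slightly less favourable NYHA percentages.
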